**18.1.3. MISSING DATA METHODS FOR PRIMARY EFFICACY VARIABLE**

For the primary endpoint of percent change from baseline to Week 12 in LDL-C values, a pattern mixture model (PMM) will be used to specify different imputation strategies depending on whether the patient is still on study treatment. Patients with missing lipid data at Week 12 who are no longer taking study treatment (defined by date of last dose of study medication is < Week 12 lab assessment date -7) can be assumed to no longer be benefitting from study medication, and their missing value(s) can be assumed to be similar to those in placebo group who remained on study and have data. To account for uncertainty, missing values will be imputed using multiple imputation via a regression based model including stratification and baseline data from placebo subjects only. In this imputation model, treatment group will not be included as a factor.

Patients with missing lipid data at Week 12 who are still taking study treatment (date of last dose of study medication is ≥ Week 12 lab assessment date -7) can be assumed to continue to benefit from study medication, and their missing value(s) can be assumed to be similar to those who remain on study treatment and have data and as a result, lipid values will be imputed based on the observed values in their randomized treatment group at Week 12. To account for uncertainty, missing values will be imputed using multiple imputation via a regression based model including treatment, stratification and baseline value.

Imputed datasets will be analyzed using the same ANCOVA model with treatment and stratification as factors and baseline LDL-C as a covariate described in [section 18.1.2](#). Approximately 200 imputed datasets will be created, with results from the analysis of each imputed dataset combined using Rubin’s method. The least squares mean (LSM) and standard error (SE) will be provided for both treatment groups, along with the placebo-corrected LSM, its 95% confidence interval (CI) and associated p-value. To account for possibility of unequal variances between the groups, the ANCOVA model will be implemented within mixed model framework where <repeated/group=> option will be used to allow separate estimation of residual variance between the groups.

Further information on the multiple imputation method is presented in [Appendix 4](#).

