**APPENDIX 4. DETAILS OF MULTIPLE IMPUTATION METHOD**

Missing Week 12 values will be imputed based on baseline values. The following table details the possible cohorts and which cohorts will be used for imputation. Missing Week 24 values will be imputed in the same way.

	Treatment	Week 12 Value	On Treatment at Week 12	Imputation Cohort(s)
1	Placebo	Missing	Yes	Cohort 5: Placebo patients with non-missing Week 12
2	BA	Missing	Yes	Cohorts 6 and 8 BA patients with non-missing Week 12
3	placebo	Missing	No	Cohort 5: Placebo patients with non-missing Week 12
4	BA	Missing	No	Cohorts 5 and 7 Placebo patients with non-missing Week 12 and not on treatment
5	placebo	Non-missing	Yes	
6	BA	Non-missing	Yes	
7	placebo	Non-missing	No	
8	BA	Non-missing	No	

Imputation code for Cohorts 1-3.

```
proc mi;
where cohort in(1,2,3,5,6,8);
class trt01pn strata;
monotone regression;
var trt01pn strata base aval;
run;
```

Imputation code for Cohort 4.

```
proc mi;
where cohort in(4,5,7);
class strata;
monotone regression;
var base strata aval;
run;
```

[figure not shown]
Version Number: 1.7  
 Version Date: 21Mar2018

Two hundred imputed datasets will be created, with results from the analysis of each imputed dataset (ANCOVA) combined using Rubin’s method.

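### Appendix 4 imputes on-treatment bempedoic acid patients from on- and off-treatment donors but on-treatment placebo patients from on-treatment donors only, which fits neither reading of SAP 18.1.3

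*SAP*

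**What the plan says.** SAP 18.1.3 divides patients with a missing Week 12 value by treatment status. A patient counts as still on treatment if the last dose falls no earlier than seven days before the Week 12 laboratory date.

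- **Still on treatment:** "their missing value(s) can be assumed to be similar to those who remain on study treatment and have data". The same sentence then bases the imputation on what was observed in the patient's own randomised arm, by a regression on treatment, stratum and baseline. Protocol 11.5 has the same two steps.
- **Off treatment, either arm:** a regression fitted to placebo subjects only, with no treatment term.

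Appendix 4 turns this into eight cohorts, using a column headed "On Treatment at Week 12". Cohorts 1 to 4 have missing values. Cohorts 5 and 6 are placebo and bempedoic acid (BA) patients with data and on treatment; cohorts 7 and 8 are their off-treatment counterparts with data. The donors for cohort 2 (BA, missing, on treatment) are "Cohorts 6 and 8 BA patients with non-missing Week 12". For cohorts 1 and 3 (placebo, missing, on and off treatment) the entry is "Cohort 5: Placebo patients with non-missing Week 12".

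The code for cohorts 1 to 3 starts its row selection "where cohort in(1,2,3,5,6,8" and models "var trt01pn strata base aval". The code for cohort 4 starts "where cohort in(4,5,7" and has no treatment variable. Appendix 4 extends the method to Week 24, and SAP 18.2.1 applies the 18.1.3 method to the key secondary endpoints.

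**The concern.** Off-treatment patients are asked to keep attending visits with fasting lipids (protocol 8.4), so cohorts 7 and 8 can be populated. The first imputation model has no term for treatment status. Any cohort 8 patient therefore pulls the fitted BA mean toward the off-drug level, and that mean is what on-treatment BA patients with missing data receive. The placebo arm has no matching step, because cohort 7 is left out.

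At stake is whether the coded primary analysis carries out the stated missing-data assumption. A programmer working from 18.1.3 and one working from Appendix 4 could produce different primary estimates. The analyses in SAP 18.2.3 do not impute, so none of them tests the donor rule.

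**Working it through.** **1. Donor sets side by side.** Here a donor is a row that helps fit the imputation model.

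| Missing cohort | Appendix 4 | 18.1.3, on-treatment assumption | 18.1.3, own-arm clause read alone |
|---|---|---|---|
| 1: placebo, on | 5 | 5 | 5, 7 |
| 2: BA, on | 6, 8 | 6 | 6, 8 |
| 3: placebo, off | 5, in a two-arm model with treatment | placebo-only model, no treatment term | same as previous column |
| 4: BA, off | 5, 7, no treatment term | placebo-only model, no treatment term | same as previous column |

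Row 2 departs from the third column and row 1 from the fourth. Row 3 departs from both. PROC MI fits one regression to all selected rows, so cohorts 6 and 8 also inform the baseline slope, stratum effect and residual variance used for cohort 3. A placebo-only model would exclude that.

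**2. Size of the cohort 8 effect.** The documents give no figure to reproduce, and the visible text has no effect size, SD, missing-data rate or discontinuation rate. All inputs here are assumptions:

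- d = effect lost when off drug: 15 to 25 percentage points
- f = off-treatment share of BA patients with data: 5% to 20%
- m = share of BA patients who are on treatment with a missing value: 1% to 10%

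Shift in the imputed on-treatment BA mean = f × d. Lowest: 0.05 × 15 = 0.75 points. Highest: 0.20 × 25 = 5.0 points.

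Shift in the treatment difference = m × f × d.

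- Lowest: 0.01 × 0.05 × 15 = 0.0075, about 0.01 points
- Middle: 0.05 × 0.10 × 20 = 0.10 points
- Highest: 0.10 × 0.20 × 25 = 0.50 points

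**3. Simulation check.** The regression imputation was simulated with 200 BA and 100 placebo patients, d = 20, residual SD 15, 200 replicates and 10 imputations each. The off-treatment share F was equal in both arms, on-treatment values were missing with probability p, and 30% of off-treatment values were missing. The analysis model was ordinary ANCOVA, not the SAP's unequal-variance version. The comparison drops cohort 8 only; cohort 3 stays where Appendix 4 puts it.

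With these definitions m = (1 − F) × p and f = 0.7F / [0.7F + (1 − F)(1 − p)]. For F = 20% and p = 5%, f = 0.14 / (0.14 + 0.76) = 0.156 and m = 0.04, so m × f × 20 = 0.124.

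| F | p | Appendix 4 | Without cohort 8 | Difference (SE) | m × f × 20 |
|---|---|---|---|---|---|
| 5% | 2% | −18.858 | −18.853 | −0.005 (0.012) | 0.014 |
| 10% | 3% | −18.090 | −18.132 | 0.042 (0.015) | 0.040 |
| 20% | 5% | −15.905 | −16.063 | 0.158 (0.026) | 0.124 |
| 20% | 10% | −16.098 | −16.373 | 0.276 (0.030) | 0.260 |

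Differences were taken before rounding. The formula agrees with the simulation within Monte Carlo error, and the first scenario shows no detectable difference.

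**4. Under no drug effect.** With d = 0 the shift m × f × d is zero.

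**The case against.** The strongest defence is that row 2 follows the operative half of 18.1.3. The on-treatment statement is only a premise. The instruction that follows points to observed values in the randomised arm and sets no on-treatment limit, and cohorts 6 and 8 are exactly the observed BA patients. A reader might infer that Appendix 4 flatly contradicts 18.1.3; because of this clause, the text does not support so strong a statement. The defence still fails to rescue Appendix 4. The clause is tied to the premise: patients "can be assumed to be similar to those who remain on study treatment and have data and as a result" are imputed that way. Read on its own, it would also bring in cohort 7 for placebo, which table and code leave out.

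Three further inferences would go too far:

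- **A threat to alpha control.** The shift is zero without a drug effect and otherwise runs toward no difference.
- **A larger effect at Week 24.** This is plausible if more patients are off drug, but the size also depends on the on-treatment missing share, and the documents give neither rate.
- **A wrong result from the row 4 label.** Its wording can be read as off-treatment placebo only, but its cohort numbers, its code and 18.1.3 agree on cohorts 5 and 7. That is editorial.

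The reach is also limited. Off-drug patients are not scheduled for apoB or hs-CRP (note to protocol Table 2), and SAP 18.2.1 analyses hs-CRP by rank methods. The on-treatment analysis in 18.2.3.3 removes cohort 8 values, and the observed-data analysis in 18.2.3.4 removes imputation. Both give partial reassurance, but neither shows what the imputed primary result would be under the stated rule.

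**Conclusion.** The point stands as a specification error in the primary analysis. Appendix 4 treats the arms differently, is inconsistent with the on-treatment assumption in SAP 18.1.3 and protocol 11.5, and matches neither reading of 18.1.3. Its handling of cohort 3 also departs from the placebo-only, no-treatment-term rule for off-treatment patients.

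The likely numerical effect is small: about 0.01 to 0.5 percentage points on the treatment difference, the upper end needing every input at its extreme. This range covers cohort 8 only; the cohort 3 departure was not quantified. Size and direction rest on assumed rates and on stopping drug doing no more than removing the drug effect. On that basis the error works against bempedoic acid and does not inflate Type I error. The reason to act is that text, table and code should define one reproducible primary analysis.

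**What to change.** Apply one donor rule across 18.1.3, the Appendix 4 table and the code. To implement 18.1.3 as stated:

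- **Cohorts 1 and 2:** use on-treatment patients of the same arm. Row 2 becomes cohort 6, and the code becomes `where cohort in (1,2,5,6)` with treatment, stratum and baseline.
- **Cohorts 3 and 4:** use the placebo-only model without treatment, `where cohort in (3,4,5,7)`. Rows 3 and 4 both become cohorts 5 and 7, labelled *placebo patients with non-missing Week 12, on or off treatment*.
- **Week 24:** use the same rule.

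Removing cohort 8 alone would not be enough, because cohort 3 would stay in a model with treatment as a factor. If all observed patients of the arm were intended for cohorts 1 and 2, use 5 and 7 for placebo and 6 and 8 for BA, and amend the assumption in 18.1.3 to say so.

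The cost is two WHERE statements, three table rows and a rerun, with slightly fewer donors for cohort 2. The SAP addendum of December 2018 reports the planned analysis as complete, so the practical step is to record the discrepancy and report the corrected run beside the planned one, labelled post hoc.

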11.5. Primary Endpoint Analysis

The primary efficacy endpoint is the percent change from baseline to Week 12 in LDL-C. Baseline is defined as the mean of the values from Week -1 (Visit S3) and predose Day 1/Week 0 (Visit T1).

The primary efficacy endpoint will be analyzed using analysis of covariance (ANCOVA), with treatment group and patient type (primary prevention; secondary prevention) as factors and

baseline LDL-C as a covariate. The ANCOVA will be performed using the FAS, with patients included in their randomized treatment group regardless of the treatment they actually received. The details of the ANCOVA model and options to account for unequal variances and group size will be described in the SAP.

Missing data for the primary endpoint will be imputed using a multiple imputation method that accounts for treatment adherence. A pattern mixture model (PMM) will be used to specify different imputation strategies depending on whether the patient is still on study treatment. Patients with missing LDL-C data at Week 12 who are no longer taking study treatment can be assumed no longer to be benefitting from study medication, and their missing value(s) can be assumed to be similar to those from placebo patients. In this instance, it is reasonable to impute LDL-C values in a model including placebo patients' data only. Patients with missing LDL-C data at Week 12 who are still taking study treatment can be assumed to continue to benefit from study medication, and their missing value(s) can be assumed to be similar to those who remain on study treatment and have data. In this instance, it is reasonable to impute LDL-C values based on the observed values in their randomized treatment group at Week 12. Details for the PMM will be described in the SAP.

To account for uncertainty, missing values will be imputed using multiple imputation. Imputed datasets will be analyzed using an ANCOVA model with the treatment and patient type (primary prevention; secondary prevention) as factors and baseline LDL-C as a covariate. Approximately 200 imputed datasets will be created, with results from the analysis of each imputed dataset combined using Rubin's method. For each type of ANCOVA (observed case; imputation via PMM), the least squares mean (LSM) and standard error (SE) will be provided for both treatment groups, along with the placebo-corrected LSM, its 95% confidence interval (CI) and associated p-value.

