#### 18.1.2. PRIMARY ANALYSIS OF PRIMARY EFFICACY VARIABLE

The null hypothesis,  $H_0$ , will be that there is no difference between bempedoic acid 180 mg/day and placebo in mean percent change from baseline to Week 12 in LDL-C. The alternative hypothesis,  $H_1$ , will be that bempedoic acid 180 mg/day is different from placebo:

$$H_0: \mu_p = \mu_b$$

$$H_1: \mu_p \neq \mu_b$$

where  $\mu_p$  and  $\mu_b$  denote the mean percent change from baseline to Week 12 in LDL-C on placebo and bempedoic acid 180 mg/day respectively.

The primary efficacy endpoint will be analyzed using analysis of covariance (ANCOVA), with treatment group and stratification factor patient type as factors and baseline LDL-C as a covariate. To account for the likelihood of unequal variances between the treatment groups, the ANCOVA model will be implemented within mixed model framework and the *<repeated/group=>* option will be used to allow estimating the residual variances separately between the groups. Model assumptions for performing ANCOVA will be assessed and if the assumptions are severely violated, non-parametric methods will be performed.

In addition, descriptive statistics will be presented for LDL-C at each visit and for change from baseline and % change from baseline.

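### The Appendix 4 code for cohorts 1-3 imputes both arms from one pooled regression, against its own arm-specific donor table and the plan's unequal-variance analysis

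*SAP*

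**What the plan says.** **Donor table, SAP Appendix 4.** Missing placebo values, on or off treatment (cohorts 1 and 3), are assigned "Cohort 5: Placebo patients with non-missing Week 12". Missing active values in patients still on treatment (cohort 2) are assigned cohorts 6 and 8, described as "BA patients with non-missing Week 12".

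**Code for cohorts 1-3, same appendix.** One PROC MI call selects both arms ("where cohort in(1,2,3,5,6,8") and fits "var trt01pn strata base aval". It has no BY statement and no treatment-by-baseline term. Missing active values in patients off treatment (cohort 4) have their own placebo-only call, which is not at issue here.

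**SAP 18.1.3.** For patients still on treatment, "lipid values will be imputed based on the observed values in their randomized treatment group at Week 12". It then says that "missing values will be imputed using multiple imputation via a regression based model including treatment, stratification and baseline value". For patients off treatment it specifies a model fitted to placebo data only and leaves treatment out as a factor.

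**Protocol 11.5.** For patients still on treatment it is reasonable to "impute LDL-C values based on the observed values in their randomized treatment group at Week 12".

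**Analysis model.** SAP 18.1.2 gives each arm its own residual variance, "To account for the likelihood of unequal variances between the treatment groups". SAP 18.1.3 repeats this for the imputed datasets.

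**Reach.** Appendix 4 imputes Week 24 in the same way, and SAP 18.2.1 carries the method to the key secondary endpoints.

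**The concern.** The regression lets the arms differ only in intercept. Baseline slope, stratum effect and residual variance are estimated from both arms together and then used to draw values for each. With 2:1 allocation the pooled variance sits closer to that of the active arm. If the arms differ in spread, imputed placebo values get too much of the active arm's spread and imputed active values get some of placebo's. The ANCOVA then estimates variances by arm from data in which part of each arm was drawn with the wrong variance. At stake are the width of the primary confidence interval and, to a small degree, the type I error. If the slopes differ too and missingness depends on baseline, the point estimate is also touched.

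There is a specification problem as well. The table and the code define different imputations for the primary analysis, so two programmers could each follow Appendix 4 and get different results.

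**Working it through.** **1. Table, text and code by cohort**

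| Cohort with missing value | Table | SAP 18.1.3 | Code |
|---|---|---|---|
| 1, placebo on treatment | placebo donors | own arm's values; one model with treatment as a term | pooled, treatment as main effect |
| 2, active on treatment | active donors (6, 8) | own arm's values; one model with treatment as a term | pooled, treatment as main effect |
| 3, placebo off treatment | placebo donors | placebo-only model, no treatment term | pooled, treatment as main effect |

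For cohorts 1-2 the code follows one sentence of 18.1.3 but not the table. For cohort 3 it follows neither.

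**2. Inputs**

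From the documents: 200 active and 100 placebo patients, two-sided 5% level, 200 imputations, separate-variance ANCOVA. The documents state no SD by arm, missing rate or standard error, so there is no figure of the plan's own to reproduce. Assumed: residual SDs of 15 and 22.5 percentage points (ratio 1.5), and a fraction *f* of 5% or 10% of each arm imputed by this code.

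**3. Approximate formula**

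This ignores covariate estimation and the 1/m term. Let s² be an arm's residual variance, n its size, and p² the pooled variance, (200·s²_active + 100·s²_placebo)/300.

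- By-arm imputation, Rubin variance of an arm's mean: s²/[(1−f)n].
- Pooled imputation: [(1−f)s² + f·p²]/n + f·p²/[(1−f)n].

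The variance of the treatment difference is the sum over arms.

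*Placebo SD 22.5, active SD 15, f = 10%:* p² = (200·225 + 100·506.25)/300 = 318.75.

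- Pooled, active: (202.5 + 31.875)/200 + 31.875/180 = 1.349.
- Pooled, placebo: (455.625 + 31.875)/100 + 31.875/90 = 5.229.
- Pooled SE = √6.578 = 2.565.
- By arm: 225/180 + 506.25/90 = 1.25 + 5.625, so SE = √6.875 = 2.622.
- Ratio 2.565/2.622 = 0.978.

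*Active SD 22.5, placebo SD 15, f = 10%:* p² = (200·506.25 + 100·225)/300 = 412.5.

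- Pooled: 2.714 + 2.896 = 5.609, so SE = 2.368.
- By arm: 2.8125 + 2.5 = 5.3125, so SE = 2.305.
- Ratio 2.368/2.305 = 1.028.

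At f = 5% the same formulas give 0.989 and 1.014. With equal SDs the two expressions are identical.

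**4. Simulation**

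Both methods were applied to the same simulated trials, with regression imputation, a separate-variance ANCOVA and Rubin's rules. There were 100 imputations (raising this to 200 in one scenario left the ratio at 0.987) and 400 to 4,000 trials per scenario. The last column uses 4,000 trials, with Monte Carlo error of about 0.35 points.

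| SD ratio, more variable arm | Imputed | SE pooled / by arm | Type I error, pooled v by arm |
|---|---|---|---|
| equal | 5% | 0.999 | – |
| 1.5, placebo | 5% | 0.987 | 5.3% v 5.0% |
| 1.5, placebo | 10% | 0.974 | 5.5% v 4.9% |
| 1.5, active | 5% | 1.014 | 4.3% v 4.7% |
| 1.5, active | 10% | 1.027 | – |
| 2, placebo | 20% | 0.929 | 6.9% v 5.4% |
| 2, active | 20% | 1.085 | 3.4% v 5.3% |

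A separate simulation with SDs of 28 and 20 (ratio 1.4) and 10% imputed agrees: 3.32/3.40 = 0.976 with placebo more variable, and 3.15/3.06 = 1.029 with active more variable.

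**5. Slopes**

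Slopes were set to differ by 6 points per baseline SD, with 10% missing, all at above-average baseline. Pooling then attenuated the treatment difference by about 0.5 percentage points. By-arm imputation was unbiased within simulation error.

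**The case against.** The best defence is that SAP 18.1.3 prescribes a regression with treatment, stratum and baseline, and the code is that regression. With treatment as a main effect, each arm's imputed level still rests on its own observed data, which is a fair reading of basing values on the randomized group. This stands for cohorts 1-2, where the conflict is between 18.1.3 and the table. It does not cover cohort 3, and it does not explain why the imputation should assume a common variance when the analysis does not.

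The exposure is also limited. Patients who stop drug are asked to keep attending for lipids (Protocol 8.4), missing off-treatment active values go to a different model, and four analyses without imputation are planned (SAP 18.2.3). So 10% through this code may be high.

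Three stronger readings are tempting and are not supported:

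- *That the primary standard error is in fact distorted.* SAP 18.1.2 calls unequal variances likely. It gives no SDs, and with equal SDs and slopes nothing changes.
- *That the error is as large as 7%.* In the SD 28/20 simulation with the active arm more variable, the pooled SE of 3.15 exceeds the empirical 2.94 by 7%. But the by-arm SE of 3.06 exceeds it by 4% as well (3.06/2.94 = 1.04). Pooling accounts for 2.9%.
- *That the slopes must differ.* That argument is strongest if the imputed variable is LDL-C in mg/dL, and Appendix 4 does not define it.

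**Conclusion.** The inconsistency is certain and can be read off the page: the cohort 1-3 code does not implement the donor table, contradicts 18.1.3 for cohort 3, and assumes a common slope and variance that the analysis model does not. Its numerical effect is conditional and small. With an SD ratio of 1.4 to 1.5 and 5% to 10% of values imputed here, the Rubin SE moves by about 1% to 3%, anti-conservatively if placebo is the more variable arm and conservatively if active is. In the ratio-1.5 scenarios where it was checked, type I error stayed between 4.3% and 5.5%. Shifts of 7% to 8.5% needed an SD ratio of 2 with 20% imputed. Any shift in the estimate needs differing slopes together with baseline-dependent missingness. The same applies to Week 24 LDL-C and the other key secondary endpoints analysed by ANCOVA. Nothing here suggests that the primary conclusion would change. It is a correction worth making because it costs almost nothing.

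**What to change.** Run the cohort 1-3 step separately by arm: add `by trt01pn;` on sorted data and remove `trt01pn` from CLASS and VAR. Placebo then uses cohorts 1, 3 and 5, and active uses cohorts 2, 6 and 8, as the table states. Amend the 18.1.3 sentence that lists treatment as a model term. If the sponsor prefers the pooled model, the table and the cohort 3 text should say so, with a reason for assuming a common variance.

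Whether cohort 8 (active, off treatment, value observed) belongs among the donors is a separate question. The table and code include it, while the text of 18.1.3 and Protocol 11.5 likens these patients to those who remain on treatment. That should be reconciled openly and not changed as a by-product of the BY statement.

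The cost is one BY statement and fewer patients per regression, at most about 100 and 200. The SAP addendum says the planned analysis is complete, so the report should state which version was run and give the by-arm result as a check.
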